### **5.5.2.7 Patient Health Questionnaire**

The PHQ-9 will be collected at V1a, V3, V5, V7 and EOT or EDV and, if applicable, UNS.

The PHQ-9 can be used for screening, diagnosing and measuring the severity of depression in stroke patients. The patient will rate on a scale from 0 (not at all) to 3 (nearly every day) how often each of the 9 symptoms occurred during the past 2 weeks. With question 9, the presence and duration of suicide ideation will be screened [6].

The PHQ-9 consists of the following questions:

Over the last 2 weeks, how often have you been bothered by any of the following problems?

1. Little interest or pleasure in doing things
2. Feeling down, depressed, or hopeless
3. Trouble falling or staying asleep, or sleeping too much
4. Feeling tired or having little energy
5. Poor appetite or overeating
6. Feeling bad about yourself - or that you are a failure or have let yourself or your family down
7. Trouble concentrating on things, such as reading the newspaper or watching television
8. Moving or speaking so slowly that other could have noticed. Or the opposite - being so fidgety or restless that you have been moving around a lot more than usual
9. Thoughts that you would be better off dead or of hurting yourself in some way

The individual scores from each item of the PHQ-9 will be added to calculate the total PHQ-9 score for each time of examination.

The PHQ-9 total score will be categorised as follows:

$\leq 4$  – minimal depression  
 $> 4$  – mild to severe depression

The individual scores from each item of the PHQ-9 will be added to calculate the total PHQ-9 score for each time of examination. The PHQ-9 score and its change from baseline will be summarised by means of descriptive statistics and differences between the treatment groups (ESL-Placebo) will be evaluated exploratively using the Wilcoxon-Mann-Whitney Test and exact Hodge-Lehmann Cis (if the SAS code runs for more than 10 minutes, maxtime=50 will be used and the approximate result will be tabulated. A higher maxtime does not lead to a change of the result).

Cumulative incidence curves of USs vs. the PHQ-9 score ( $\leq 4$ ,  $> 4$ ) will be displayed graphically by time after randomisation and treatment group.

PHQ-9 question 9 (related to suicidal ideation) will also be evaluated for the safety set.

The following statistical outputs will be presented:

Table 15.2.8.1.1 Summary of PHQ-9 Total Score – Full Analysis Set

Table 15.2.8.1.2 Summary of PHQ-9 Total Score – Per Protocol Set

The default summary statistics for the PHQ-9 total score will be presented by visit slots by treatment group at Baseline, V3, V5, V7, EOT, EDV (if applicable) and Endpoint.

Table 15.2.8.2 Summary of PHQ-9 Question 9 Score – Safety Set

The default summary statistics for the PHQ-9 Question 9 score will be presented by visit slots by treatment group at Baseline, V3, V5, V7, EOT, EDV (if applicable) and Endpoint.

Table 15.2.8.3.1 Analysis of PHQ-9 Total Score Differences – Full Analysis Set

Table 15.2.8.3.2 Analysis of PHQ-9 Total Score Differences – Per-Protocol Set

The Hodges-Lehmann estimate of location shift and the corresponding 95% CIs including the p-value will be presented by visit slots for V3, V5, V7 and Endpoint for ESL-Placebo.

Figure 15.2.4.1 Cumulative Incidence Curves of Unprovoked Seizures using Kaplan-Meier Curves by PHQ-9 Total Score – Full Analysis Set

Figure 15.2.4.2 Cumulative Incidence Curves of Unprovoked Seizures using Kaplan-Meier Curves by PHQ-9 Total Score – Per-Protocol Set

Cumulative incidence curves of USs using Kaplan-Meier curves displayed by time after randomisation and treatment group for each category of the PHQ-9 total score.

Listing 16.2.3.5 Patient Health Questionnaire (PHQ-9)– Enrolled Set

The PHQ-9 items and total score data will be listed by treatment group.

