This is a multicentre, double-blind, randomised, placebo-controlled, parallel-group trial in patients with acute intracerebral haemorrhage with a CAVE score \geq 3 or an acute ischaemic stroke with a SeLECT score \geq 6.

At the first visit (screening/baseline, V1a), patients will undergo several examinations to check eligibility. The next visit (V1b) has to be performed within 96 hours after primary stroke occurrence. After eligibility has been confirmed, patients will be randomised (randomisation ratio 1:1) to treatment with ESL 800 mg (Group A) or placebo (Group B). Patients can receive therapies for stroke treatment according to local clinical practice at any time during the trial.

Patients will start treatment with the investigational medicinal product (IMP), i.e. ESL or placebo, within 96 hours after primary stroke occurrence at V1b. They will continue treatment until Day 30 after randomisation and then be tapered off. Thereafter, patients will be followed up until 18 months after randomisation. Patients can concomitantly receive antiepileptic therapies, except commercially available ESL or oxcarbazepine, until Day 30. Concomitant antiepileptic therapies have to be discontinued and down-titration has to be started according to the respective Summary of Product Characteristics (SmPC). If the antiepileptic drugs (AEDs)/benzodiazepine are not already discontinued before, down-titration must be started on Day 31 at the latest.

If one or more AS(s) occur(s) within 7 days after primary stroke, this will not result in change of IMP dose. Patients having a first US will discontinue IMP treatment and will be treated at the discretion of the investigator until 18 months after randomisation, except with commercially available ESL.

Further visits will be performed 7 days (V2, on-site), 37 days (V3, on-site), 12 weeks (V4, telephone), 26 weeks (V5, on-site), 38 weeks (V6, telephone), 52 weeks (V7, on-site), 64 weeks (V8, telephone) and 78 weeks (End of Trial [EoT] visit, on-site) after V1b. Patients

who discontinue trial participation prematurely will be asked to come to the site for an early discontinuation visit (EDV). Unscheduled visits (UNS) will be performed at the discretion of the investigator, as necessary.

Patients or their caregivers (as applicable) will be instructed to contact the site immediately after a seizure has occurred and to document seizure information in the patient diary.

Number of patients (planned):

Screened:	220
Randomised:	200

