12. EoT: End of Trial visit
13. Only applicable, if EDV is performed before V3.
14. Only applicable if performed prior to V2 and only for patients who were unable to give informed consent at V1a.
15. The patients will be reminded via phone call on the working day before Day 30 to either take the last tablet on Day 30 (those with ESL 400 mg) or to take half a tablet from Day 31 to Day 37 (those with ESL 800 mg) and (if applicable) to start the down-titration of AED/benzodiazepines according to the respective SmPC on Day 31, if not already discontinued before.
16. Seizure records based on diary entries may be applicable in case of on-site visits, only.

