#### **2.1.3 Safety Objectives**

The safety objectives of this trial are to assess the effect of ESL treatment on:

10. Treatment emergent adverse events (TEAEs) incl. findings from physical and neurological examinations
11. Laboratory parameters
12. Vital signs
13. Electrocardiogram (ECG)
14. Suicidal ideation and behaviour, assessed by PHQ-9 (question 9)

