**Table 3: Visit Slotting**

Visit Slot/ Label	Target Day	Description
V1a	-	Screening/baseline, within 120 hours after stroke, or since last time seen well
V1b	1	Day 1, within 120 hours after stroke, or since last time seen well
V2	8	Closest non missing assessment to target day between study day 2 and 31
V3	38	Closest non missing assessment to target day between study day 32 and 71
V4	85	Closest non missing assessment to target day between study day 72 and 171
V5	183	Closest non missing assessment to target day between study day 172 and 242
V6	267	Closest non missing assessment to target day between study day 243 and 353
V7	365	Closest non missing assessment to target day between study day 354 and 437
V8	449	Closest non missing assessment to target day between study day 438 and 533
EOT	547	Closest non missing assessment to target day between study day 534 and >547

EDV	EDV	Early discontinuation visit
-----	-----	-----------------------------

If, for any variable, a visit was not scheduled (e.g. V4 for vital signs), the respective measurement will be assigned to the visit slot with the closest target day where a visit was scheduled. If two measurements fall into that slot, the closest one to target day will be used.

If, for any safety variable, V1b is not scheduled and a measurement is taken on Study Day 1, this measurement will be slotted to V2 if the assessment was done after first IMP intake.

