## **Endpoint value**

The endpoint value for an efficacy variable is defined as the last non-missing value collected after first intake of IMP before or at the respective endpoint (within the time window of interest i.e. 6 month-period, 12 month-period and 18 month-period).

The endpoint for a safety variable is defined as the last non-missing value collected after first intake of IMP that is no baseline value.

**Absolute change from baseline** will be calculated as

$$\text{Absolute Change from Baseline at Visit } X = \text{Value at Visit } X - \text{Baseline Value}$$

**Relative change from baseline (%)** will be calculated as

$$\text{Relative Change from Baseline at Visit } X = \frac{\text{Value at Visit } X - \text{Baseline Value}}{\text{Baseline Value}} \times 100$$

Note: Patients with a baseline value of '0' will be excluded from the calculation of relative change.

See section 5.4.1 for the definition of first and last IMP intakes.

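### PHQ-9 question 9 is first repeated at V3, whose two-week recall covers at most 14 of 37 treatment days, and Table 15.2.8.2 has no on-treatment count of patients with suicidal ideation

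*SAP*

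**What the plan says.** SAP 2.1.3 and the protocol synopsis list suicidal ideation and behaviour, assessed by PHQ-9 question 9, among the safety objectives. No other instrument is named. SAP 5.6 repeats the item but gives it no subsection. Its one dedicated output is Table 15.2.8.2, described in SAP 5.5.2.7.

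- **Timing.** "The PHQ-9 will be collected at V1a, V3, V5, V7 and EOT or EDV and, if applicable, UNS". The schedules in both documents agree. V2 has NIHSS, laboratory tests, ECG and examinations, but no PHQ-9.
- **Recall.** The patient rates "how often each of the 9 symptoms occurred during the past 2 weeks".
- **Dosing period (SAP 2.5).** One-tablet patients take the full dose on Days 1-30 and half a tablet on Days 31-37. Half-tablet patients stop on Day 30.
- **Table.** "The default summary statistics for the PHQ-9 Question 9 score will be presented by visit slots by treatment group". Its rows are baseline, the four scheduled post-dose PHQ-9 visits, the early discontinuation visit where it applies, and an Endpoint.
- **Endpoint (SAP 4.8).** "The endpoint for a safety variable is defined as the last non-missing value collected after first intake of IMP that is no baseline value".
- **V3 slot (SAP Table 3).** "Closest non missing assessment to target day between study day 32 and 71".
- **TEAE window (SAP 5.6.1).** From first IMP intake to 14 days after the last.

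**The concern.** The objective asks what ESL treatment does to suicidality, but the named instrument is first repeated around the end of treatment. Every later scheduled administration comes months after dosing has stopped. The planned table then has no row that gathers on-treatment answers and no count of patients who gave a positive one.

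At stake is how a quiet table would be read. Similar arms in Table 15.2.8.2 could mean that ESL has no effect on ideation, or that most of the treatment period lay outside the recall of the scheduled questionnaires. The table as specified does not let a reader tell these apart. Question 9 also concerns thoughts, and SAP 5.5.2.7 itself describes it as screening for ideation. It therefore cannot answer the behaviour half of the objective.

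**Working it through.** **Plan's own days.** Study day = offset from V1b + 1. V2: 7 + 1 = 8. V3: 37 + 1 = 38. EoT: 78 × 7 + 1 = 547. All match the schedules.

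**V3 recall.** Take the 14 days before the visit and count those on IMP.

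| V3 on | Days recalled | Full dose (Days 1-30) | Taper (Days 31-37) | One-tablet: on IMP | Half-tablet: on IMP |
|---|---|---|---|---|---|
| Day 38 | 24-37 | 7 | 7 | 14 of 37 (38%) | 7 of 30 (23%) |
| Day 42 | 28-41 | 3 | 7 | 10 of 37 (27%) | 3 of 30 (10%) |

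Counting the visit day itself shifts the recall by one day (Day 38: 6 full-dose plus 7 taper days). SAP Table 2 gives the V3 window as 38+4. Parts of the schedules print 38±4, possibly through text conversion. A Day 34 visit would recall Days 20-33: 11 full-dose and 3 taper days, so 14 of 37, or 11 of 30 for half-tablet patients. A value late in the V3 slot (Day 71) recalls Days 57-70, with no day on IMP.

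**Patients who stop IMP early but stay in the trial.** If the last dose is before Day 24, a Day 38 questionnaire recalls no day on IMP.

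**TEAE window.** 30 + 14 = Day 44 and 37 + 14 = Day 51. V3 on Days 38-42 lies inside both. V5 (Day 183), V7 (Day 365) and EOT (Day 547) lie outside. The window also fits the recall: a questionnaire on Day 51 recalls Days 37-50, and one on Day 44 recalls Days 30-43, so each still includes the last dose day.

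**Endpoint row for a completer.** 547 − 37 = 510 days after the last taper dose; 547 − 30 = 517 days for half-tablet patients.

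**Slotting (SAP 4.5).** V2 is not a PHQ-9 visit, so an unscheduled questionnaire on, say, Day 15 goes to the nearest slot with a scheduled PHQ-9, which is V3. When two values share a slot, the one closer to Day 38 is used. The Day 15 answer then leaves the table and remains only in Listing 16.2.3.5.

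**What the statistics show (SAP 4.1).** The set includes the maximum, so any positive answer in a visit row appears as a maximum of 1 or more. The number of patients is not given, and the mean of an integer score prints to one decimal. As an illustration with the planned 100 per arm, one patient scoring 1 gives 1/100 = 0.01 and four give 4/100 = 0.04. Both print as 0.0 with a maximum of 1. Elsewhere the SAP does summarise worst values: minimum post-baseline sodium, and laboratory shifts to the worst post-baseline value (5.6.2). Question 9 has no equivalent.

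**The case against.** The other side has several good points.

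- **The objective concerns ESL treatment, not full-dose days.** The taper is still IMP, so for one-tablet patients on Day 38 the fair figure is 14 of 37 days; 7 of 30 alone would understate it. This stands, and the working uses it.
- **There are other routes.** Adverse events are recorded at every visit, including V2, and TEAEs are tabulated by preferred term and arm (Tables 15.3.1.2.1 and 15.3.1.4.1). The neurological examination, done at V2, includes mental status. PHQ-9 is given at EDV and is optional at unscheduled visits. A reader might infer that suicidality on ESL is hardly measured, or that a patient with early ideation is never asked. The documents do not support that. The gap is in the scheduled use of the named instrument. The protocol text supplied is a synopsis and schedule, so how adverse events are elicited cannot be judged.
- **Positive answers are not hidden.** The maximum shows that one exists, and Listing 16.2.3.5 gives every item by arm. This stands; what is missing is the count.
- **Endpoint is one extra row.** V3 and EDV have their own rows, and an early withdrawal's Endpoint may be an on-treatment EDV value. The 510 to 517 days apply to completers only.
- **The schedule can no longer be repaired.** SAP 2.6 and 8 record that recruitment ended early, and the revision history shows that the blind data review meeting had been held. Missed V2 answers cannot be recovered.

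None of this supplies an on-treatment count by arm.

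**Conclusion.** The point holds as a limitation of timing and a gap in the table specification. Question 9 is not scheduled at V2, and V3 is the only scheduled post-dose questionnaire inside the SAP's own TEAE window for patients who complete IMP. V3 recalls 14 to 10 of 37 treatment days for one-tablet patients (7 to 3 of them at full dose) and 7 to 3 of 30 for half-tablet patients. Table 15.2.8.2 does not say how many patients per arm reported ideation on or near treatment.

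The figures assume the 38+4 window, dosing as scheduled, and recall of the 14 days before the visit. Under 38±4 the full-dose overlap rises to at most 11 days, which leaves the conclusion unchanged. The documents do not justify saying that the safety objective goes unanswered or that a signal would be concealed, because adverse event tables, the maximum and the item listing remain. The SAP change is still worth making: it is cheap, uses data already collected, and can be fixed before unblinding.

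**What to change.** In SAP 5.5.2.7 and Table 15.2.8.2, before unblinding:

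1. Add by arm n (%) of patients with question 9 at 1 or more, at baseline and at each visit.
2. Add by arm n (%) with any value of 1 or more from first IMP to 14 days after last IMP. Use all scheduled, EDV and unscheduled questionnaires without slotting. Show the number of patients with at least one value in the window, since some early stoppers will have none.
3. Define the question 9 Endpoint as the last value in that window, and label V5, V7 and EOT as off-treatment follow-up.
4. State that question 9 covers ideation only, and refer to the existing TEAE tables by preferred term for behaviour.

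The cost is one revised table and a few lines of text. The limitation is few on-treatment questionnaires per patient, so the new rows will be sparse and should be read with the recall coverage stated beside them.

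Only if patients were still to be treated would a schedule change help. Question 9 at V2 would add recall of about Days 1-7. Adding it to the existing call on the working day before Day 30 (about Days 15-28 for a Day 29 call) would still leave about Days 8-14 uncovered. That call is described only as a dosing and down-titration reminder, so screening would be a new task for it.

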### **5.5.2.8 Overall Survival**

Overall survival (time to death relative to the date of randomisation) will be analysed and presented by means of the Kaplan-Meier estimates (including censored data e.g. withdrawals) after 6 months (Day 182), 12 months (Day 365) and 18 months (Day 547) for the survival rates including pointwise CI, log-rank test as well as estimates for 25% percentile, median, and 75% percentile survival time and corresponding CI.

For this purpose, the following SAS code will be used:

```
ODS OUTPUT Quartiles=quartiles;
ODS OUTPUT ProductLimitEstimates=limit;
ODS OUTPUT HomTests= tests;
PROC LIFETEST DATA=<dataset> METHOD=KM TIMELIST= 182 365 547;
  TIME <Time to death>*<Status> (0);
  STRATA <Treatment group> /TEST=LOGRANK;
RUN;
```

Kaplan-Meier plot for overall survival will be presented.

The following statistical outputs will be presented:

Table 15.2.9.1 Overall Survival – Full Analysis Set

Table 15.2.9.2 Overall Survival – Per Protocol Set

Number and percentage of patients who died and patients censored will be tabulated. The time to death in days will be presented by estimates for 25% percentile, median, and 75% percentile and corresponding CI; means of the Kaplan-Meier estimate after 6, 12 and 18 months for the time to death and corresponding pointwise CI and the p-value of a log-rank test will be presented.

Figure 15.2.5.1 Overall Survival – Full Analysis Set

Figure 15.2.5.2 Overall Survival – Per Protocol Set

The Kaplan-Meier Product Limit Estimate and simultaneous equal precision 95%-Confidence bounds will be presented.

### **5.6 Safety Analysis**

Safety will be assessed by evaluation of the following variables:

- TEAEs incl. findings from physical and neurological examinations

- Laboratory parameters (haematology and biochemistry, including eGFR and coagulation, urinalysis)
- Vital signs
- ECG
- Suicidal ideation and behaviour (as per PHQ-9, question 9)

The safety set will be used for the analysis of safety data.

### 5.6.1 Adverse Events

AEs will be coded according to the Medical Dictionary for Regulatory Activities (MedDRA®) Version as defined in the Data Management Plan.

Adverse event data includes:

- adverse event name
- start date and time
- ongoing? (yes/no)
- stop date and time, if applicable
- severity (mild, moderate, severe)
- frequency (single event, intermittent, continuous)
- causal relationship to IMP (not related, unlikely, possible, probable, definite)
- action taken with IMP (dose increased, dose not changed, dose reduced, drug interrupted, drug withdrawn, unknown, not applicable)
- other action taken (none, medication required, tests required, hospitalisation required or prolonged, withdrawn from the trial, other, including specification)
- outcome (recovered/resolved, recovering/resolving, not recovered/not resolved, recovered/resolved with sequelae, fatal, unknown)
- seriousness (yes/no)

All AEs will be presented in listings.

Summaries of adverse events will include AEs defined as **treatment-emergent adverse events (TEAEs)**, defined as AEs with the first onset or worsening after the first IMP intake until 14 days after the last IMP intake. AEs not considered treatment-emergent according to this definition or with missing data will be medically reviewed during the blind data review meeting and will be considered treatment-emergent if appropriate.

If the relationship to IMP is missing, the event will be classified as unrelated, if it started before first IMP intake. In all other cases it will be assumed to be possibly related.

If the start date of an AE is incomplete or missing, it will be assumed to be treatment-emergent except if the incomplete start date or the stop date indicates that the event started prior to the first IMP intake or later than 14 days after last IMP intake.

Adverse events will be further assigned to the following categories:

- **Serious Adverse Events (SAEs):** defined as AEs considered by the investigator as serious, including AEs with an unknown or missing seriousness assessment.
- **Related TEAEs:** TEAEs with a causal relationship to IMP assessed as “possible” or “probable” and “definite”, including events with missing IMP relationship assessment.
- **Unrelated TEAEs:** TEAEs with a causal relationship to IMP assessed as “not related” or “unlikely”.
- **Severe TEAEs:** TEAEs assessed as “severe” in severity, including events with missing severity assessments.
- **TEAEs leading to discontinuation of IMP:** TEAEs for which “action taken with study medication” is indicated as “drug withdrawn”.

- **TEAEs leading to dose reduction:** TEAEs for which “action taken with IMP” is indicated as “dose reduced”
- **TEAEs requiring medication:** TEAEs for which “action taken with study medication” is indicated as “medication required”.
- **TEAEs leading to death:** TEAEs documented as having a “fatal” outcome.
- **Ongoing TEAEs at the end of the trial:** TEAEs documented without an end date of the TEAE.

The **duration of the AE** will be calculated from the start date (or onset) to the AE stop date. If the start or stop dates of the AE are incomplete or AE is still ongoing at the end of the study, duration of AE will not be calculated.

The following statistical output will be provided:

Table 15.3.1.1 Overall Summary of TEAEs – Safety Set

An overview of TEAEs:

- TEAEs
- Non-serious TEAEs
- Serious TEAEs
- Related TEAEs
- Related Serious TEAEs
- Severe TEAEs
- TEAEs leading to discontinuation of IMP
- TEAEs leading to dose reduction
- TEAEs requiring medication
- TEAEs leading to death
- Ongoing TEAEs at the end of the trial

will be displayed by treatment group and in total for the patients in the safety set.

Table 15.3.1.2.1 Incidence of TEAEs – Safety Set

Table 15.3.1.2.2 Incidence of Non-Serious TEAEs – Safety Set

Table 15.3.1.2.3 Incidence of Serious TEAEs – Safety Set

Table 15.3.1.2.4 Incidence of Related TEAEs – Safety Set

Table 15.3.1.2.5 Incidence of Related Serious TEAEs – Safety Set

Table 15.3.1.2.6 Incidence of TEAEs Leading to Discontinuation of IMP – Safety Set

Table 15.3.1.2.7 Incidence of TEAEs Leading to Dose Reduction – Safety Set

Table 15.3.1.2.8 Incidence of TEAEs Requiring Medication – Safety Set

Table 15.3.1.2.9 Incidence of TEAEs Leading to Death – Safety Set

TEAEs will be summarised by treatment group and in total by displaying the numbers of adverse events, as well as counts and percentages of patients having experienced adverse events. Percentages will be based on the number of patients in the safety set. SOCs and PTs within each SOC will be ordered by descending number of adverse events in the total column.

Table 15.3.1.3.1 Incidence of TEAEs by Maximum Severity – Safety Set

Table 15.3.1.3.2 Incidence of Related TEAEs by Maximum Severity – Safety Set

Table 15.3.1.3.3 Incidence of Serious TEAEs by Maximum Severity – Safety Set

TEAEs will be summarised as above within each severity category (mild, moderate, severe).

Table 15.3.1.4.1 Incidence of Preferred Term: TEAEs – Safety Set

Table 15.3.1.4.2 Incidence of Preferred Term: Serious TEAEs – Safety Set

Table 15.3.1.4.3 Incidence of Preferred Term: Related TEAEs – Safety Set

Table 15.3.1.4.4 Incidence of Preferred Term: Serious Related TEAEs – Safety Set

Table 15.3.1.4.5 Incidence of Preferred Term: TEAEs Leading to Discontinuation of IMP – Safety Set

Table 15.3.1.4.6 Incidence of Preferred Term: Most Frequent ( $\geq 2\%$  of patients in any treatment group) TEAEs – Safety Set

Frequency counts and percentages of PTs will be summarised for each treatment group and in total. Percentages will be based on the overall number of PTs in the safety set. PTs will be ordered by descending percentages in the total column.

Listing 16.2.4.1.1 Adverse Events: MedDRA Coding

MedDRA system organ class and preferred terms assigned to each reported AE name will be displayed.

Listing 16.2.4.2.1 Serious Adverse Events – Enrolled Set

Listing 16.2.4.2.2 AEs Leading to Discontinuation of IMP – Safety Set

Listing 16.2.4.2.3 AEs Leading to Death – Enrolled Set

All AEs will be displayed by patient including the PT of an AE, start and stop dates, date of last IMP intake and other characteristics of AEs.

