## 2.6 Sample Size

Based on retrospective historical data, 26% of patients are expected to experience the first US (i.e. failure rate) within the first 6 months after stroke with standard of care. As this is a pilot trial, no empirical estimate of the treatment effect in patients randomised to ESL is available. For the purpose of sample size estimation, the trial is planned to have at least 80% power to demonstrate a significantly lower failure rate under ESL compared to placebo under the following assumptions:

- An expected failure rate (including death and other reasons of missing data before the first US) of 26% under placebo within the first 6 months after stroke
- An expected failure rate (including death and other reasons of missing data before the first US) of 8% under ESL within the first 6 months after stroke

Under these assumptions 100 randomised patients per treatment arm will ensure a power of the trial of at least 80% to demonstrate a significantly lower failure rate under ESL compared to placebo by means of a two-sided chi-square test on a 5%-level of significance.

Recruitment was terminated before reaching the estimated sample size.

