### **4.1 General Methodology and Presentation of the Results**

The default summary statistics for quantitative (continuous) variables will be

- the number of patients with data at the visit (n),
- number of patients with missing data (nmiss),
- mean,
- standard deviation (SD),
- median,
- first quartile (Q1) and third quartile (Q3)
- minimum (min) and maximum (max)

for patients with data.

Mean, median, and the quartiles will be presented to one more decimal place than the raw value. The minimum and maximum values will be presented with the same decimal precision as the raw value. SD will be reported to two decimal places greater than the original value.

For qualitative (categorical) variables, the number (n) and percentage (%) of patients with non-missing data per category will be the default frequency tabulations. Where appropriate and present, the number of missing values will be displayed as “Missing” category.

Percentage values are to be presented to one decimal place, for example, 52.3%.

The denominator used for calculation of the percentages will be specified in a footnote to the tables for clarification.

All reported p-values will be two-sided. No adjustment for multiplicity will be performed.

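### Three safety displays are mis-specified: six preferred-term tables use the wrong denominator, one adverse event category points to the wrong field, and three laboratory tables leave out V2

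*SAP*

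**What the plan says.** **Preferred-term tables (SAP 5.6.1).** One rule covers Tables 15.3.1.4.1 to 15.3.1.4.6, all titled as incidence: "Percentages will be based on the overall number of PTs in the safety set". The abbreviation list defines PT as preferred term, so this is not shorthand for patients. For Tables 15.3.1.2.x the same section gives "counts and percentages of patients having experienced adverse events. Percentages will be based on the number of patients in the safety set". Table 15.3.1.4.6 keeps terms that reach 2% "of patients in any treatment group) TEAEs".

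**TEAEs requiring medication (SAP 5.6.1).** The definition is "TEAEs for which “action taken with study medication” is indicated as “medication required". The discontinuation category uses the same field label: "TEAEs for which “action taken with study medication” is indicated as “drug withdrawn". The dose-reduction category names the collected field directly: "TEAEs for which “action taken with IMP” is indicated as “dose reduced". In the list of adverse event data at the start of the section, the value *medication required* occurs only under the field for other action taken.

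**Descriptive laboratory tables (SAP 5.6.2).** Laboratory samples are scheduled at V1a, V2 and V3, and at the early discontinuation visit if that comes before V3. Tables 15.3.2.1.1 to 15.3.2.1.3 are to show V1, baseline, V3, the early discontinuation visit and Endpoint. V2 is not listed, and V1 is not a slot in Table 3 of section 4.5.

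**The concern.** A reader takes an incidence table to show the share of patients with an event. Dividing by preferred terms gives something else, and the SAP does not say whether terms are counted as records within an arm, as records over both arms, or as distinct terms. Two sets of incidence figures for the same terms would then disagree, and a table could print percentages below its own inclusion threshold. Depending on the reading, the comparison between arms can be distorted too.

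The second slip could leave Table 15.3.1.2.8, and its row in Table 15.3.1.1, empty although the data were collected. The third would drop the mean change from baseline in haematology, biochemistry (including sodium and eGFR) and coagulation at the one scheduled post-baseline laboratory visit within Days 1 to 30.

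**Working it through.** The plan states no figure on this point, so there is none to reproduce. The documents give no adverse event counts, and section 2.6 records that "Recruitment was terminated before reaching the estimated sample size". All counts in part 1 are therefore assumptions.

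**1. Denominator.** Let N be the patients in an arm, k the patients with a given term, m the term records per patient in the arm, and r the records per affected patient. Patient incidence is k/N. The printed percentage is:

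- records counted per arm: k·r/(m·N) = (k/N)·(r/m), whatever the sample size
- records pooled over arms: k·r/(m₁N₁ + m₂N₂); with equal arms, (k/N)·r/(m₁ + m₂)
- D distinct terms, r = 1: k/D

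Take a term in exactly 2.0% of an arm's patients, with r = 1. It meets the cut-off of Table 15.3.1.4.6.

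| Reading | Assumption | Printed |
|---|---|---|
| Per arm | m = 1.5 | 2.0/1.5 = 1.3% |
| Per arm | m = 2 | 2.0/2 = 1.0% |
| Per arm | m = 3 | 2.0/3 = 0.7% |
| Pooled, equal arms | m = 1.5 in both | 2.0/3.0 = 0.7% |
| Pooled, equal arms | m = 3 and 1.5 | 2.0/4.5 = 0.4% |
| Distinct terms, 2 of 100 patients | D = 50, 120, 200 | 4.0%, 1.7%, 1.0% |

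Now compare two arms of 100 with a true incidence of 6.0% against 3.0% (r = 1 unless stated):

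- Per arm, m = 3 and 1.5: 6/300 = 2.0% and 3/150 = 2.0%. The difference disappears.
- Per arm, m = 1.5 in both: 6/150 = 4.0% and 3/150 = 2.0%. The ratio is kept.
- Pooled, m = 3 and 1.5: 6/450 = 1.3% and 3/450 = 0.7%. The ratio is kept.
- Pooled, same m, but r = 2 in the first arm: 12/450 = 2.7% and 3/450 = 0.7%. The ratio is 4 where the truth is 2.

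The pooled reading also distorts when the arms differ in size. With 60 and 40 patients, 3 and 2 affected (5.0% in each) and m = 2 in both, there are 120 + 80 = 200 records, and the table prints 3/200 = 1.5% against 2/200 = 1.0%.

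**2. Field and value.** The field for action taken with IMP has seven listed values, and *medication required* is none of them (0 of 7). The field for other action taken has six, and it is one of them (1 of 6). The label in the definition is not the exact name of either field. Its use with *drug withdrawn*, a value of the IMP field, shows which one it stands for. A filter on that field for *medication required* returns no events.

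**3. Visits.** Reading V1 as V1a, the scheduled laboratory visits missing from the descriptive tables reduce to V2: one of the two scheduled post-baseline visits, in three tables. From Table 3 of the SAP, the V2 slot covers Days 2 to 31, plus Day 1 samples taken after the first dose. The V3 slot covers Days 32 to 71 with target Day 38. Since 32 > 30, no V3 value falls within Days 1 to 30. The last scheduled taper dose is on Day 37 (section 5.4.1), one day before the V3 target. Endpoint is the last available value after first intake (section 4.8), so it will usually be the V3 value.

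**The case against.** The best case for the plan is that nothing essential is lost. Five of the six preferred-term tables have a patient-based counterpart in Tables 15.3.1.2.x, and the sixth is a subset of Table 15.3.1.2.1. Percentages of terms over a total of terms could be a deliberate event-share display, and section 4.1 promises that "The denominator used for calculation of the percentages will be specified in a footnote to the tables for clarification". The figures in the working rest on assumed counts, and the most striking one needs the per-arm reading, while the plan's wording fits the pooled reading at least as well.

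On the second item, the value exists in only one field, so a careful programmer would find it. On the third, V1 may simply be a slip for V2. The table shells are separate documents that were not available here. V2 results also reach the abnormality tables, the worst-value shift tables, the hyponatraemia table and the listings. A V3 sample taken on Days 32 to 37 can still fall within the taper.

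Most of this stands as a limit on impact. It does not make the text right. A footnote discloses a denominator without correcting it. An event-share display fits neither the incidence titles nor a cut-off defined on patients. The pooled reading keeps the ratio between arms only if the arms are equal in size and have equal records per affected patient. A specification should not rely on the programmer to repair it, and correct shells would still contradict the SAP.

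**Conclusion.** The concern holds in all three parts, with minor to moderate consequences. Part 1 is the most serious: followed as written, it prints percentages that are not patient incidences on any reading and that can contradict the 2% cut-off of Table 15.3.1.4.6. The direction of the error is clear from the text, but its size depends on m, r, arm sizes and term counts that the documents do not give.

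Part 2 would empty one adverse event category if the label is mapped as its use elsewhere implies. Part 3 leaves V2 out of the descriptive statistics and change from baseline in three tables, unless V1 was meant as V2. The primary endpoint, every hypothesis test and the collected data are untouched.

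**What to change.** Make three edits to the SAP before unblinding:

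1. Tables 15.3.1.4.1 to 15.3.1.4.6: base percentages on the number of safety-set patients in each treatment group and in total, and state that a patient counts once per preferred term. Reword the preceding sentence on counts of terms to match.
2. TEAEs requiring medication: define them as TEAEs with *medication required* recorded under other action taken.
3. Tables 15.3.2.1.1 to 15.3.2.1.3: list baseline, V2, V3, the early discontinuation visit where applicable, and Endpoint. V1a need not appear separately, because baseline is the last value before first intake and V1a is the only scheduled sample before dosing.

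The cost is three one-line changes and matching updates to the shells where needed. All the data are already collected.
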